Developing a Team-Delivered Intervention for Smoking and Hazardous Drinking for Primary Care Veterans With Cardiovascular Diseases (CARE)

ClinicalTrials.gov ID NCT05275582

Sponsor VA Office of Research and Development

PI: [name]

Study Protocol

Version Approval Date: 11/20/2023

Overview of CARE-PACT and CARE-PCMHI Study and Research Activities

Conditions

CARE-PACT: Patient aligned care team (PACT) providers will conduct their typical PACT appointment, and at the end will alert the behavioral health education (BHE) to join the appointment. The PACT provider will introduce the BHE; provide education about personalized health risks and outcome expectancies of changing using guided handouts. and encourage engagement with the BHE on the optional self-monitoring portion of Cardiovascular Risk Education – in PACT (CARE-PACT). The BHE will then escort the patient to a new exam room and describe the self-monitoring component of CARE-PACT that will target task self-efficacy. Instructions and materials for self-monitoring will be provided, and participants will be instructed about the follow-up appointments to occur two weeks and four weeks after CARE-PACT.

CARE-PCMHI: CARE-PCMHI is nearly identical to CARE-PACT, except that participants will not participate in the conjoint appointment. Primary Care Mental Health Integration (PCMHI) indicates that the participant will have their normal PACT appointment, and then will be contacted by a member of the study team to schedule a solo appointment with the BHE. At that 25-30 minute appointment, the BHE will provide education about personalized health risks and outcome expectancies of changing using guided handouts. The BHE will then describe the optional self-monitoring component of CARE that will target task self-efficacy. Instructions and materials for self-monitoring will be provided, and participants will be instructed about the follow-up appointments to occur two weeks and four weeks after CARE.

Potential participants will be identified as such:

- 1) Direct referral from a primary care provider OR a data pull using Corporate Data Warehouse from the VA Informatics and Computing Infrastructure (VINCI) of eligible patients assigned to the provider for care OR
- 2) research staff will manually “scrub” PACT panels by looking ahead at a provider’s scheduled PACT visits in the coming months and looking in each patient’s electronic medical record (EMR) to assess for signals of eligibility.
 - a. We are request approval to access 10,000 records from these various means (provider panel scrubbing, CDW data pull, or direct referral) in order to meet our eventual recruitment goals.
 - b. The primary eligibility criteria will include (a) seeing that the patient carries a diagnosis of a cardiovascular condition in their Problem List or in any of their last 2 years of PACT data encounter codes; (b) screened positive for smoking or hazardous alcohol use at least their two most recent PACT visits (i.e., two positive tobacco use screens or AUDC ≥ 3 for women or 4 for men on the Primary Care Annual Screeners).

Data from potential participants (i.e., name, contact information, last 4 of their social, whether they are a smoker or drinker, cardiovascular condition(s), and date of pact appointment) will be entered into a password-protected database that will then be used to identify patients to screen for eligibility.

Below is a description of the various CARE intervention and research activities, from the patient’s perspective. Each of these will be described in detail below this list.

1. As early as 6 months before PACT appointment: Receive letter regarding study
2. As early as 12 weeks before PACT appointment: Receive telephone call to screen.
3. Between four weeks to one hour before the PACT appointment, 60-minute baseline session in person, via telephone, or via VVC
4. CARE-PACT participants: PACT appointment will include a 5-minute CARE-PACT conjoint appointment
 1. CARE-PCMHI participants: normal PACT appointment without additional conjoint appointment

5. Sometime following PACT appointment: 20-25 minute meeting with the BHE to explain the optional self-monitoring task, set up follow-up visits, and screen for safety
 1. Participants in the CARE-PCMHI condition will be contacted by telephone to schedule this appointment after their PACT appointment. We will attempt to contact them twice by telephone, and if they do not respond to this we will send a letter to them requesting that they contact the study staff to reschedule the appointment. We chose two calls + a letter because this is the standard practice in VA PCMHI clinics for no-shows/missed appointments.
6. For next 2 weeks after CARE: optional self-monitoring using app/diary
7. 10-minute booster session with BHE using telephone, in-person or VA Video Connect (VVC) format
8. For next 2 weeks: optional self-monitoring using app/diary
9. 10-minute booster session with BHE using telephone, in-person or VA Video Connect (VVC) format
10. Around 6-weeks after PCP appointment, complete 60-minute follow up assessment
11. Around 3 months after PCP appointment, complete 30-minute follow up assessment
12. Around 6 months after PCP appointment, complete 30-minute follow up assessment

PACT Appointment and CARE-PACT Conjoint Appointment: After participants in the CARE-PACT condition complete the baseline assessment, they will complete their normal PACT appointment, including the CARE-PACT conjoint meeting for CARE-PACT participants. During this meeting, Veterans will be introduced by their PACT provider to the BHE, and the PACT provider will go over the relevant handouts to the patient that describe Health Risks and Expectancies related to smoking/drinking and the Veteran's heart condition. The BHE's role is to ensure understanding between the Veteran and PACT provider. The conjoint portion of CARE-PACT will take approximately 5 minutes.

Solo BHE/PCMHI Appointment: Following the PACT appointment, the patient will meet alone with the BHE or PCMHI provider to learn about the at-home self-monitoring app that they can choose to use. Though this is not mandatory, it will be encouraged. The BHE will explain that as part of the CARE trial, Veterans will be asked to complete four weeks of the self-monitoring procedure (~5 minutes per day) and will participate in two telephone or in-person appointments (10 minutes) at the 2- and 4-week mark (more in detail below).

During the solo visit with the BHE, participant safety (i.e., suicidal intent/ideation) will be assessed using the VA's current PCMHI mandated screening and follow-up tools: The Columbia Suicide Severity Index screener, and if positive, VA's full Comprehensive Suicide Risk Evaluation. These measures were chosen as they mirror what would occur in a typical PACT handoff to a PCMHI provider, and therefore if CARE-PACT is eventually implemented in PACT settings, the standard risk assessment protocol will be embedded into its protocol. Should any imminent risk issues be present, a licensed psychologist (i.e., the PI or other CIH psychologists) will be notified and consulted regarding next steps (i.e., if a patient needs to be brought to the emergency department for admission).

4 Weeks Self-Monitoring Protocol: As above, patients will be introduced to and given the option to complete 4 weeks of self-monitoring using a data collection app called Expiwell. Expiwell is an app used for researchers/healthcare systems to deliver assessments and receive data from participants in their natural environment. We will ask participants to complete 1 daily morning assessment (each morning when they wake), which asks questions about the previous day specifically pertaining to health behaviors such as their drinking and smoking. During the day, the app will also (at random intervals) prompt Veterans to respond to 4 assessments. These assessments will also inquire about any recent smoking/drinking, mood, and context (e.g., if the participant is or is not with friends, at work, etc).

Expiwell is available on the app store for participants to download onto their Smartphone If the participant does not have a smartphone, the participant will be provided an iPod to use for the duration of the study. This iPod was purchased specifically for this study, and will have Expiwell already installed. It will also have an admin password which will prevent the participant from downloading additional apps. Participants will be asked to create an Expiwell account (which will ask them to enter their name/email address). In the event that they do want to use the app but do not want to enter their name, we will have a list of pseudonyms and false email addresses that they can use instead. If they choose to create an account either with their real information or with a pseudonym, they will then receive a code from our study team, which will enroll them into our study. Data entered from our study questions will be automatically stored on Expiwell's secure server, and will be downloaded by study staff from this server on a weekly basis. The assessments that we are asking participants to do as part of the study will **contain no sensitive information, will only be identified in the data set by a random ID number, and participants will have the option to delete their data from Expiwell at any time they choose.** Although sensitive information (i.e., name/email address) is asked of participants to create an Expiwell account, this is an optional part of the study and is not VA data, as we will not have access to it and Veteran's are entering the information.

If a participant is not comfortable using the app, we will provide a backup paper-pencil assessment packet for them to complete the assessments. This option will only be offered if a participant expresses that they do not wish to use the app.

Telephone, VVC, or In-Person Booster Sessions: At 2 and 4 weeks post-CARE-PACT, participants will have a 10-minute booster phone call or in-person appointment (their choice). During this booster, they will discuss how the monitoring is going, and what (if any) insights were gained as a result of engaging in the monitoring. If the participant no-shows or does not answer the call, we will make multiple efforts to contact them within the next week to reschedule.

6-Week, 3-, and 6-Month Follow-ups: Participants will be asked to complete follow-up assessments at 1.5, 3, and 6 months following their PCP appointment assessing intention/motivation to change, tobacco and/or alcohol dependence, treatment history and quitting history, and perception of their healthcare team. **The 6 week assessment takes approximately 60 minutes and participants will receive \$30. The 3 and 6 month assessments take approximately 30 minutes, for which participants will receive \$20 each.** If participants do not respond to phone calls to complete these assessments, they may be sent a letter requesting that they contact the lab. Participants may receive a letter prior to these assessment appointments that remind

Inclusion Criteria [source of data in brackets]

1. Veteran patients \geq age 18 seen in PACT at the Buffalo VAMC [EMR]
2. Upcoming PACT appointment [EMR]
3. A diagnosis of cardiac disease, including coronary artery disease, hypertension, hyperlipidemia, OR ischemia [EMR]
4. Positive alcohol or tobacco use screen for at least **two consecutive years** (including most recent) for [EMR]:
 - a. Smoking (i.e., Answered "Yes" on the Annual VHA Tobacco Use Screening Questionnaire) AND/OR
 - b. Hazardous drinking (Alcohol Use Disorders-Consumption [AUD-C] \geq 4 for men or 3 for women)
5. Currently smokes at least one cigarette per day OR currently scores in a range indicating hazardous drinking on the Alcohol Use Disorders Identification Test (AUDIT) [telephone screen]
6. Currently reports on 1 to 10 scale having no greater than high-moderate (defined as ≥ 8) intention to change their drinking and/or smoking behavior [telephone screen;]

Exclusion Criteria [source of data in brackets]

1. Disorientation at time of eligibility (i.e., delirium, acute psychosis, dementia, severe intoxication) [EMR, telephone screen, or clinical judgment at the time of the in person appointment]
2. Unable to read or understand English [telephone screen]
3. Non-Veteran status [EMR]

Measures

The following outcome measures for the future larger RCT will be piloted in this study. These will be administered at the Baseline Appointment as well as the follow-up appointment:

- 1) Readiness to Change Questionnaire: 12-item measure¹¹⁶ ($\alpha=0.73-0.85$) of current intention to change. This scale has been shown to predict future behavior change and has been used in drinkers and smokers. (Main Outcome)
- 2) Readiness and Confidence: visual analog scale (ruler) for (a) readiness to change smoking and/or drinking behaviors as well as (b) confidence in changing¹¹⁷. Rulers such as these have been shown to predict behavior change for tobacco use as well as alcohol use. The rulers will range from 1 (not at all ready/confident) to 10 (very ready/confident to make a behavior change). (Main Outcome)
- 3) Measures of alcohol quantity/frequency (Secondary Outcome)
- 4) Subscales *General Quality Assessment* and *Care and Concern* from the Patient Satisfaction Survey¹¹⁹: measures perception of quality of care by patients and predictive validity for engaging in healthcare changes. Reliability for the overall scale ($\alpha=0.81$) and the subscales is high ($\alpha=0.85, 0.88$) (secondary outcome).¹

Data Analysis Plan

Descriptive statistics will be calculated for all patient variables, including demographics, outcome variables, recruitment, feasibility, and survey responses. The primary patient outcomes that we will preliminarily evaluate are readiness to change via a ruler and a questionnaire, and secondary measures include substance use and satisfaction. Primary analysis of these variables will be repeated measures analysis of variance with calculation of both between-groups (CARE-PCMHI vs. CARE-PACT) and within-groups (pre- and post-intervention) effects sizes. Intent-to-treat analyses to account for attrition will be conducted using the last value carried forward methodology which is the recommended method to minimize risk of bias. Though we are statistically underpowered to detect large differences between groups, the statistical methodology described here will be piloted for a larger grant submission. Additional outcomes of this work included looking at descriptive statistics of feasibility of data collection processes, fidelity and training related outcomes, and other feasibility outcomes.

¹ Other measures were collected that were not primary or secondary outcomes.

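### Does timing the 6-week assessment from the PCP appointment spoil the comparison when CARE-PCMHI starts later?

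*Combined protocol and SAP*

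**What the plan says.** The list of intervention and research activities times the first follow-up as "Around 6-weeks after PCP appointment, complete 60-minute follow up assessment" (item 10). Items 11 and 12 use the same anchor for 3 and 6 months. The follow-up section repeats it: "Participants will be asked to complete follow-up assessments at 1.5, 3, and 6 months following their PCP appointment".

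The Conditions section starts the arms differently.

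- **CARE-PACT:** the behavioral health educator (BHE) joins the end of the primary care visit, and the solo part follows directly: "The BHE will then escort the patient to a new exam room and describe the self-monitoring component of CARE-PACT".
- **CARE-PCMHI:** the patient has an ordinary primary care visit and afterwards "will be contacted by a member of the study team to schedule a solo appointment with the BHE". The content comes only then: "At that 25-30 minute appointment, the BHE will provide education about personalized health risks and outcome expectancies of changing using guided handouts". Item 5.1 describes the booking effort: "We will attempt to contact them twice by telephone, and if they do not respond to this we will send a letter to them". No maximum delay is given.

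In CARE-PCMHI the boosters count from the later session: "follow-up appointments to occur two weeks and four weeks after CARE". The Data Analysis Plan specifies repeated measures analysis of variance with between-group effect sizes and "within-groups (pre- and post-intervention) effects sizes". It does not say which follow-up is the post-intervention one.

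**The concern.** The assessment clock starts at the primary care visit in both arms, but the intervention clock starts there only in CARE-PACT. As planned, a CARE-PACT participant finishes the second booster about two weeks before the 6-week assessment. A CARE-PCMHI participant who waits three weeks for the solo visit would be assessed before the second booster.

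The readiness questionnaire and rulers are the main outcomes, and they are what the education and self-monitoring aim to move. If many CARE-PCMHI participants were still in the intervention at 6 weeks, part of an apparent CARE-PACT advantage could come from unfinished treatment in the other arm. The CARE-PCMHI effect size labelled post-intervention would also include people who had not finished. This pilot is meant to inform a larger application, so a misread effect size could carry forward.

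**Working it through.** The plan states no figure here to reproduce, so the check is timeline arithmetic in weeks from the primary care visit.

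**Inputs**
- First follow-up: week 6, stated as approximate (activity list, item 10).
- Start of CARE: week 0 in CARE-PACT; week d in CARE-PCMHI (Conditions). The documents do not give d, so I assume 0 to 6.
- Length of intervention: 4 weeks from the start of CARE (Conditions; solo appointment section).
- Booster slippage: s weeks. The booster section limits renewed contact efforts to the following week but sets no limit on the date of the rescheduled booster, so s is also an assumption.
- 3-month assessment: taken as week 13.

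**Formulas**
- End of intervention = d + 4 + s.
- Gap at 6 weeks = 6 - (d + 4 + s) = 2 - d - s.
- Gap at 3 months = 13 - (d + 4 + s) = 9 - d - s.
- Time since CARE began, at week 6 = 6 - d.

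**Results with boosters on time (s = 0)**

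| d (weeks) | End of intervention (week) | Gap at 6 weeks | Weeks since CARE began, at week 6 | Gap at 3 months |
|---|---|---|---|---|
| 0 (CARE-PACT) | 4 | +2 | 6 | +9 |
| 1 | 5 | +1 | 5 | +8 |
| 2 | 6 | 0 | 4 | +7 |
| 3 | 7 | -1 | 3 | +6 |
| 4 | 8 | -2 | 2 | +5 |
| 6 | 10 | -4 | 0 | +3 |

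A negative gap means the assessment precedes the last booster. With boosters on time this needs d above 2. If the last booster slips one week (s = 1), it needs d above 1. If both slip a week and the delays add up (s = 2), the gap in CARE-PACT itself falls to 2 - 0 - 2 = 0. Overlap is therefore mainly, but not strictly only, a CARE-PCMHI matter.

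**The obvious alternative: make 3 months the post-intervention contrast**
- It removes the overlap for every d in the table.
- Time since the last booster stays unequal: 9 weeks in CARE-PACT against 6 in CARE-PCMHI at d = 3, the same 3-week difference as at week 6 (+2 against -1).
- Attrition would probably be higher, and the plan carries the last value forward. Some 3-month values would then be 6-week scores, which brings the problem back.
- The 3-month session is planned at 30 minutes against 60 at 6 weeks. The Measures section refers to a single follow-up appointment. The follow-up section lists intention and motivation at all three time points, but does not confirm that both readiness instruments are in the shorter session.

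**The case for a change.** The best case for a change is that the imbalance is built in, runs in one direction and affects the main outcomes. Counting slow access as part of the pathway justifies the common anchor, but it does not make a score taken before the final booster post-intervention. Without delay data, a reader cannot separate the effect of the conjoint visit from that of an earlier start. The remedy looks cheap: name the visit and derive one date variable.

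Much of this is right. The timing conflict is possible on the plan's own schedule, and the within-group label would be inaccurate for anyone assessed early.

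The inference of bias between arms does not stand. CARE-PCMHI is a separately booked visit, and the protocol says its two calls and a letter follow usual practice in those clinics for missed appointments. Under an intent-to-treat comparison of two delivery routes, a later start is a consequence of the route. The documents do not state this rationale, but it is a reasonable reading. Timing each arm from its own start of CARE would equalise exposure but remove that consequence from the comparison.

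Treating 6 weeks as the post-intervention score is also an inference. The activity list places that assessment after the second booster, which shows the intended order, and its approximate timing leaves some room to keep it.

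**Conclusion.** No change to the plan. A 6-week score can precede the last booster when the CARE-PCMHI delay plus any booster slippage exceeds 2 weeks. With a combined delay of 2 weeks or less, none does. The documents do not say how often the limit is passed, so the size of any effect on the readiness scores cannot be stated.

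The between-arm comparison at equal time from the primary care visit remains valid as a comparison of pathways. What is left is a labelling gap in the within-group effect size, which analysts fill sensibly by stating the visit used and describing the 6-week score by time since the primary care visit. Tabulating by arm the days to the solo session, and the share of 6-week assessments made before the second booster, would help readers but changes no estimate. Moving the main contrast to 3 months is a debatable trade-off with no clear gain, in a pilot that describes its outcome evaluation as preliminary and underpowered.

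This rests on three assumptions: CARE-PACT starts at the primary care visit as the Conditions section describes (item 5 of the activity list is looser), the delay lies within the 0 to 6 weeks examined, and 3 months is about 13 weeks.

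### Last value carried forward is the only stated method for attrition and is wrongly described as minimizing bias; it can distort the readiness effect sizes in either direction

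*Combined protocol and SAP*

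**What the plan says.** The Data Analysis Plan says that intent-to-treat analyses for attrition will be done "using the last value carried forward methodology which is the recommended method to minimize risk of bias". It cites no reference and states no assumption about why data are missing. It also gives no expected attrition rate, second method or sensitivity analysis, and no other section supplies them.

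The outcomes affected are the main ones: "The primary patient outcomes that we will preliminarily evaluate are readiness to change via a ruler and a questionnaire". Their primary analysis is "repeated measures analysis of variance with calculation of both between-groups (CARE-PCMHI vs. CARE-PACT) and within-groups (pre- and post-intervention) effects sizes". The section on the 6-week, 3- and 6-month follow-ups schedules "follow-up assessments at 1.5, 3, and 6 months following their PCP appointment" and provides for letters to participants who do not answer assessment calls, so some non-response is foreseen. The Data Analysis Plan concedes low power but says that "the statistical methodology described here will be piloted for a larger grant submission".

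The plan does not say whether values are carried forward in the primary repeated measures ANOVA or only in a separate intent-to-treat analysis.

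**The concern.** Carrying the last value forward (LOCF) assumes that a participant's readiness stops moving on the day contact is lost. A trial designed to move readiness over several visits has no reason to assume this. Anyone lost after baseline is scored as exactly zero change; anyone lost after week 6 keeps the week-6 score to month 6. The filled-in values are then analysed as if they had been observed.

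Effect sizes are a planned product of this pilot, both within and between groups, and the method is meant to be taken into a larger study. A wrong rationale written here can therefore affect both the estimates used to plan that study and the way it is analysed. The direction of the error is not fixed, so LOCF cannot be defended as reliably conservative either.

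**Working it through.** **Inputs.** The documents supply the method, the outcomes and the visit schedule. They give no sample size, SD, gain, alpha or dropout rate, so there is no stated figure to reproduce. All numbers below are assumptions chosen to show the range.

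**1. Within-group gain; dropouts would respond like completers; loss before week 6.** A share d is scored as zero change, so reported gain = true gain × (1 − d). For a true gain of 0.50 SD:
- 10% loss: 0.50 × 0.9 = 0.45
- 20% loss: 0.50 × 0.8 = 0.40
- 30% loss: 0.50 × 0.7 = 0.35
- 40% loss: 0.50 × 0.6 = 0.30

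**2. Between-group difference, equal loss.** True gains of 2 and 1 points with 20% loss in both arms: (2 − 1) × 0.8 = 0.8 instead of 1.0.

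**3. Between-group difference, unequal loss, no true difference.** False difference = gain × (difference in loss). Assume a gain of 2 points in both arms, SD 2.5 and pre-post correlation 0.5. That gain is 2 / 2.5 = 0.80 SD. The false-positive rates come from 10,000 simulated trials per setting, using a t-test on change scores (the group-by-time test for two time points).

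| Loss, arm A vs arm B | False difference (points) | False positives, 20 per arm | False positives, 100 per arm |
|---|---|---|---|
| 20% vs 20% | 0.0 | 5.1% | 4.6% |
| 10% vs 15% | 2 × 0.05 = 0.1 | 5.4% | 6.2% |
| 10% vs 20% | 2 × 0.10 = 0.2 | 5.5% | 8.9% |
| 10% vs 30% | 2 × 0.20 = 0.4 | 8.6% | 22.5% |
| 30% vs 10% | −0.4 | 8.8% | 23.1% |

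Hand check of 10% vs 30% at 100 per arm:
- The SD of true change is 2.5 × √(2 × (1 − 0.5)) = 2.5.
- The variance of LOCF change is (1 − d) × 6.25 + d(1 − d) × 4, which is 5.985 at 10% and 5.215 at 30%.
- The standard error is √(11.2 / 100) = 0.335, so the false difference is 0.4 / 0.335 = 1.2 standard errors. The two-sided rejection rate is about 22%, in line with the simulation.

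An observed-data analysis under the same assumption stays within 0.02 points of zero, with false-positive rates of 4.6% to 5.3%.

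With the smaller gain of 0.50 SD used in step 1, the false difference is 0.05 SD at 10% vs 20% (5.2% and 6.8% false positives at 20 and 100 per arm). At 10% vs 30% it is 0.10 SD (6.2% and 12.3%).

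**4. Fading gain.** Take 2 points at week 6 falling to 0.5 at month 6, with 20% leaving after week 6. With random loss, LOCF reports 0.8 × 0.5 + 0.2 × 2 = 0.8. If low week-6 scorers leave more often (20% on average), it reports 0.63 (simulated). Likelihood estimation gives 0.50 to 0.52 in both cases. The overstatement depends on loss coming after week 6. In a simulation with loss spread over all visits and related to the last score, and readiness going from 0.50 SD at week 6 to 0.20 SD at month 6, LOCF reported 0.17 and 0.15 SD at 21% and 36% missing. There it understated.

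**5. Score-related dropout over four visits** (100,000 per arm, correlation 0.5, dropout dependent on the last observed score).
- True change 0.50 SD in both arms, 21% vs 36% missing: false difference 0.08 SD by LOCF, 0.00 by likelihood.
- True difference 0.30 SD, 29% missing in each arm: 0.23 by LOCF, 0.29 by likelihood.
- No true change, 29% missing: LOCF still shows −0.06 SD within each arm, because low scorers leave and their regression toward the mean goes unseen.

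**6. Where LOCF is right.** If the 20% who leave after baseline truly do not change, the true mean gain is 2 × 0.8 = 1.6 points and LOCF reports 1.6. An observed-data analysis reports 2.0, and a missing-at-random model would share that error.

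**The case against.** The strongest reply is that this is a small pilot and the practical effect is modest. The plan calls itself underpowered even for large differences. If large means 0.8 SD, that implies about 25 per arm or fewer, so the 100-per-arm column does not describe this trial. At 20 per arm a standardized difference has a standard error of about √(2/20) = 0.32, against which a shift of 0.05 to 0.10 SD is small. The plan states no alpha and makes no confirmatory claim. All of this stands, and the 100-per-arm figures are relevant only to a future larger study that inherits the method.

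Unequal loss is not shown either. CARE-PCMHI participants must be reached by telephone to arrange the solo appointment, which could cost contact, but assessments follow the same schedule in both arms. With equal loss and equal change, the between-group bias is zero.

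Three points of reading also have force:
- The ANOVA may be meant to run on observed data, with LOCF as a second analysis, in which case two contrasting results would be reported. The text does not settle this.
- The within-group contrast is described as pre- and post-intervention. If it stops at week 6, the fading-gain case cannot arise.
- Participants may miss one visit and return, whereas most of the illustration treats loss as permanent.

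These points change the size of the illustration. They do not rescue the statement that LOCF is recommended to minimize bias, which nothing in the documents supports.

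**Conclusion.** The concern holds. The rationale is wrong as written, and the plan has no assumption, alternative or sensitivity analysis to set against it. Within-group effect sizes are biased whenever dropouts' mean readiness moves after they leave. Between-group effect sizes are biased unless the product of dropout share and mean later change is the same in both arms.

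The size cannot be fixed from the documents. Under the assumptions shown, the within-group gain loses 10% to 40% of its value at 10% to 40% early loss, and false between-group differences are roughly 0.05 to 0.10 SD for a 0.50 SD gain. The sign can reverse. Confidence is high on the wording and the principle; the magnitudes are only as good as their assumed inputs. The point should be fixed, mainly because the effect sizes and the method are intended to feed a larger study.

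**What to change.** In the Data Analysis Plan:

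1. Delete the clause calling LOCF the recommended method.
2. Make the primary analysis a likelihood-based mixed model for repeated measures on all observed visits from every participant, by assigned arm, with arm, visit and arm-by-visit terms. Enter baseline as the first visit so that participants with baseline data only are kept. Use REML with small-sample degrees of freedom, and name a simpler covariance structure as fallback.
3. Derive both the within-group and between-group effect sizes from this model, and say which visits each one refers to.
4. State the missing-at-random assumption, and report missingness by arm and visit.
5. Add one simple not-at-random sensitivity analysis, for example one in which dropouts are assumed to show no gain. Step 6 of the working shows why it is needed. Keep LOCF at most as a labelled sensitivity analysis.

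The cost is wording and a different model call; no new data or patients are required. The downsides are that a covariance structure must be chosen, the missingness assumption must be stated openly, and one extra sensitivity run is needed.
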